### **Warnings and Precautions**

Warnings and precautions include the following Thyroid C-cell Tumors, Acute Pancreatitis, Acute Gallbladder Disease, Serious Hypoglycemia, Heart Rate Increase, Renal Impairment, Hypersensitivity Reactions, and Suicidal Behavior and Ideation.

### **Adverse Reactions**

Most common adverse reactions, reported in greater than or equal to 5% are: nausea, hypoglycemia, diarrhea, constipation, vomiting, headache, decreased appetite, dyspepsia, fatigue, dizziness, abdominal pain, and increased lipase. These will be reviewed with the participants.

### **Availability**

Liraglutide will be ordered directly from Novo Nordisk by the investigational pharmacy and shipped directly to the investigational pharmacy.

### **Ordering**

The study drug will be purchased from Novo Nordisk by the Investigational Pharmacy.

Product will be shipped to the investigational pharmacy and over labeled as an IP. The label will include address and telephone number, the protocol number, IP name, dosage form and strength (where applicable), amount of IP per container, lot number, expiration date (where applicable), medication identification/kit number, dosage instructions, storage conditions, and required caution statements and/or regulatory statements as applicable, as per local

regulations. Additional information may be included on the label as applicable per local regulations.

### **Accountability**

Only the pharmacist or designee will dispose study drug. A record of drug dispensed and administered to each patient must be maintained. The pharmacist will document the dose dispensed in the appropriate study records which will be reviewed during monitoring visits. In addition, the pharmacist needs to maintain an inventory log of all IP delivered, stored, dispensed and destroyed (including expiry date and batch number).

### **Destruction**

The sponsor (or designee) will review with the investigator and relevant site personnel the procedures for documenting receipt of IP, as well as the procedures for counting, reconciling IP, and documenting this process. Used (and/or empty) syringes of enoxaparin will be destroyed locally. Unused syringes will be destroyed locally after sponsor's approval for destruction. Documentation of all used and unused drug disposal must be maintained on site for review during monitoring visits.

## STUDY PLAN AND PROCEDURES

### Study Population

We will enroll 45 adolescents/young adults age 15-39 who present at any of the Principal Investigator's clinics where routine care is provided or may be recruited from the Yale New Haven Community via methods described below. 15 lean controls and 30 obese patients will be enrolled. We will enroll controls (lean) subjects (lean adults and lean adolescents) who are at risk for developing obesity (i.e. individuals with a family history of obesity or metabolic disease).

### Screening Procedures

Subjects will be identified and recruited from the local community via recruiting personnel in the Yale Center for Clinical Investigation (YCCI) and from the Yale Pediatric Obesity Clinic and the Yale Diabetes Center. We will utilize existing YCCI methods of recruitment including, fliers, web advertising, Yale research websites, and HelpUsDiscover. Potential participants will be initially screened for inclusion and exclusion criteria by phone by the research coordinator, and then, if initial study criteria are met, will be invited for an in-person visit at the Yale outpatient research unit (CSRU) or hospital research unit (HRU). Healthy lean and obese participants will be frequency matched on age, race/ethnicity and sex.

### Inclusion Criteria

1. 15-39 years old
2. Lean (BMI 18.5-24.9 kg/m^2) with normoglycemia with fasting plasma glucose (FPG) <100 mg/dL, 2-hour post oral glucose tolerance test (75gm glucose) glucose level <140 mg/dL and glycosylated hemoglobin (HbA1c) <5.7% **or**
3. Obese (BMI 30-45 kg/m^2) with or without prediabetes (insulin resistance), which is defined as two of the following:
  - a. FPG <126 mg/dL
  - b. 2-hour post oral glucose tolerance test (75gm glucose)
  - c. glucose level <200 mg/dL
  - d. HbA1c <6.5%
4. Ingest >=5 sugar sweetened beverages per week
5. Weight stable for at least 6 months
6. Able to read and write in English
7. Able to provide written and verbal informed consent

### Exclusion Criteria

1. Current active participation in a weight loss program or weight loss of >=10% of total body weight during the previous 6 months
2. Prior bariatric surgery or current gastric balloon
3. Following a vegetarian/vegan diet or dieting/restricting food due to significant food allergies, including but not limited to lactose intolerance and celiac disease
4. Significant medical condition such as cardiac or pulmonary disease, coagulopathy, gastrointestinal disorder, known history of Type 1 or Type 2 diabetes, current psychiatric disorders (including suicidal ideation and depression), current eating disorders (DSM-IV criteria), neurological injury or illness
5. Current use of weight-loss medications or supplements, psychiatric medications or anti-hyperglycemic medications (stable dose of metformin for > 6 months is acceptable)
6. History of or family history of multiple endocrine neoplasia type 2 (MEN-II) or medullary

thyroid cancer, alcoholism, or previous history of pancreatitis

7. Females who are pregnant or lactating, or who are unwilling to use proper contraception or remain abstinent,

### **Consent Process**

Research staff and investigators permitted to consent patients will describe the trial in detail including the data collection requirements, risks, procedures, and alternative treatments. Patients will be made aware that they are under no obligation to participate, that failure to participate will not adversely affect their care, and that they may withdraw consent at any time. Data will continue to be collected until the patient withdraws consent to use it. They will be given an opportunity to ask questions and have these answered to their satisfaction. The consent form will then be signed and dated by both the patient and the study personnel obtaining consent. If there are any questions regarding competence, the trial will not be offered to the patient. The consent process will be documented in the medical record.

### **Study Entry/Registration**

Eligibility will be determined by the PI and/or research team using an eligibility checklist. Once a patient is confirmed eligible and consent is obtained the patient will be assigned a unique study ID. The study ID will be used when the patient is registered into OnCore, Yale's Clinical Trials Management System and included on all related study documents. Subjects will be entered into OnCore by the study research team.

## TREATMENT REGIMEN WITH LIRAGLUTIDE

To minimize side effects; liraglutide will be titrated over the first month: starting at a dose of 0.6mg daily for 7 days, increasing to 1.2mg on day 8 for the next 7 days, increasing to 1.8mg on day 15 for the next 7 days, increasing to 2.4mg on day 22 for the next 7 days, and then increasing to 3.0mg on day 29 and continuing this dose for the remainder of the study (12-16 weeks total). This titration schedule (Table 1) will serve as a guide for study clinicians for liraglutide titration. Liraglutide will not be titrated up any faster than the above table outlines. If a participant experiences side effects (such as nausea and vomiting) the study drug will be titrated up more slowly by the study clinicians with close oversight, guidance, and approval from [name] (the study PI). If a subject is not able to increase dose to 3.0mg (due to side effects such as nausea or vomiting), they will be maintained on the highest dose they are able to tolerate, at a minimum of 1.2mg. If the subject is not able to tolerate a dose of at least 1.2mg, the medication will be discontinued and the subject will not continue in the study.

The participant will be provided with an information sheet detailing the study visits and the titration schedule (Appendix 3).

The study drug will be purchased from Novo Nordisk.

**Table 1: Dose Titration Over One Month**

Drug	Day	Dose/ Potency	Dose Frequency	Route	Treatment Period
Liraglutide	1-7	0.6mg	1x daily	Subcutaneous	1 week
Liraglutide	8-14	1.2mg	1x daily	Subcutaneous	1 week
Liraglutide	15-21	1.8mg	1x daily	Subcutaneous	1 week
Liraglutide	22-28	2.4mg	1x daily	Subcutaneous	1 week
Liraglutide	29-35	3.0mg	1x daily	Subcutaneous	Until 12 - 16 week MRI

### Administration

The medication is administered once daily subcutaneously via an injection pen. Each study participant will be taught how to administer the medication by the PI who will follow-up with each subject at specified interval time points as outlined in Appendix 1 to ensure that participants are tolerating the liraglutide and adhering to taking the medication daily. The participant's first administration will be observed to ensure that it is being done properly.

### Discontinuing Liraglutide

If a subject is not able to tolerate the medication at all due to persistent vomiting or intolerable nausea, the medication will be discontinued and the subject will not continue in the study. If the subject's mood changes while participating in the study, as assessed by PHQ-9, the PI will contact the subject and assess whether they need intervention and determine if they can continue in the study or if the drug should be discontinued.

## **Holding the Dose**

Liraglutide will be stopped temporarily if ANY the following occur:

- Persistent vomiting or nausea
- Moderate-severe dehydration (as a result of nausea/vomiting)
- Significant persistent abdominal pain
- Other side effects which the participant attributes to starting study drug

## **Restarting the Dose**

- If participant is amenable to trying the study drug again, the medication will be restarted within 4 days with phone call follow up to assess tolerability. If participant is not able to tolerate the study drug on re-initiation then they will not continue in the study. If the participant does not want to participate in the study at any time point, they may withdraw from the study.
- If the participant withdraws from the study at any point, they will be asked to complete the end of study questionnaires, dietary recalls and to return for a final weight, body composition measurement and end-of-study blood work. If the participants complete these visits, they will be compensated the same as if these visits had been completed at the end of the study.

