#### **Duration of Therapy**

For Obese patients, Liraglutide will be administered daily for 12-16 weeks. If any of the following occur, the medication will be stopped:

- Pancreatitis (severe abdominal pain, increased amylase/lipase)
- Severe dehydration
- The participant chooses not to continue in the study

Lean controls will not be given study drug.

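### The restart rule lets liraglutide resume after a hold for abdominal pain with no required investigator review or enzyme result, and severe dehydration is both a hold and a stop event

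*Combined protocol and SAP*

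**What the plan says.** Holding the Dose lists four kinds of event that lead to a temporary stop. Two matter here: "Significant persistent abdominal pain" and "Moderate-severe dehydration (as a result of nausea/vomiting".

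Restarting the Dose then gives one rule for all of them: "If participant is amenable to trying the study drug again, the medication will be restarted within 4 days with phone call follow up". The call is there to assess tolerability. If the drug is not tolerated on re-initiation, the participant leaves the study.

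Duration of Therapy lists events for which the drug must be stopped, with no mention of restarting. They include "Pancreatitis (severe abdominal pain, increased amylase/lipase" and "Severe dehydration", alongside the participant's own decision to leave.

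The protocol recognises the hazard. Warnings and Precautions names "Acute Pancreatitis, Acute Gallbladder Disease". Adverse Reactions opens its list with "Most common adverse reactions, reported in greater than or equal to 5% are" and ends it with "abdominal pain, and increased lipase". Exclusion Criteria bars anyone with previous pancreatitis.

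The protocol gives two schedules for on-treatment safety labs. Safety Laboratory Procedures and Assessments has amylase and lipase at week 0 and at the end of study (week 12-16). The liraglutide paragraph of Minimizing Risks has safety labs, covering pancreatic function, at weeks 4, 8 and 12-16.

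**The concern.** The restart rule does not distinguish between reasons for the hold. After significant persistent abdominal pain it asks for no investigator assessment, no resolution of symptoms and no laboratory result. Raised enzymes form part of the pancreatitis stop criterion, so that criterion cannot be fully checked until someone draws blood, and no for-cause draw is written for a hold. Staff who follow the restart section as written could re-expose a participant, possibly a minor, while pancreatitis is still an open question.

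The second problem is independent of the first. For severe dehydration caused by nausea or vomiting, staff have two instructions: hold and restart, or stop. The protocol does not say which takes precedence.

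**Working it through.** The protocol gives no figure to reproduce here. The check has three parts: a comparison of the text, a test of whether routine labs would supply the missing result, and a rough count of how often the situation might arise.

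**Text comparison**

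| Event | Holding / Restarting the Dose | Duration of Therapy |
|---|---|---|
| Abdominal pain | Significant and persistent: hold, then restart within 4 days if willing | Pancreatitis, described by severe pain and raised enzymes: stop |
| Moderate dehydration from nausea or vomiting | Hold, then restart within 4 days if willing | Not listed |
| Severe dehydration from nausea or vomiting | Hold, then restart within 4 days if willing | Stop |

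Significant persistent pain and severe pain are not defined apart, so the enzymes are the objective element separating a hold from a stop. Elsewhere the authors wrote in the principal investigator's decision when they wanted it: Treatment Regimen with Liraglutide requires approval for slower titration after side effects, and Discontinuing Liraglutide requires a decision after a mood change. The restart step has no equivalent.

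**Would a scheduled draw fall in the 4-day window?**

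Assumptions: week *n* is day 7*n*; a hold on day *d* allows restart up to day *d* + 4; all treatment days are weighted equally; treatment lasts 84 days (12 weeks) or 112 days (16 weeks); the end-of-study draw counts. A draw on day *D* falls in the window when *D* − 4 ≤ *d* ≤ *D*, so each draw covers 5 hold days.

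- Minimizing Risks schedule (days 28, 56 and end): 3 × 5 = 15 hold days covered. 15/84 = 17.9% and 15/112 = 13.4%, so 82.1% to 86.6% of hold days have no scheduled draw.
- Safety Laboratory Procedures schedule (end only): 5 hold days covered. 5/84 = 6.0% and 5/112 = 4.5%, so 94.0% to 95.5% have none.

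The coverage figures are upper limits, because restart may come before day 4 and a result takes time to return.

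**How often might an abdominal-pain hold occur?**

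The protocol does not say. Take its 5% floor for abdominal pain of any severity, and assume that between 10% and 100% of those cases meet the hold trigger. The second range is an assumption with no source in the document.

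- Lower end: 0.05 × 0.10 = 0.005 per participant; 30 × 0.005 = 0.15 expected; chance of at least one = 1 − 0.995^30 = 14.0%.
- Upper end: 0.05 × 1.00 = 0.05 per participant; 30 × 0.05 = 1.5 expected; chance of at least one = 1 − 0.95^30 = 78.5%.

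**The case against.** The best defence is that the restart section should not be read alone. The stop rule is unconditional, so nothing in the restart section authorises treatment in recognised pancreatitis. Willingness is a natural consent condition and need not displace clinical judgement, and a for-cause draw is not barred. Clinician contact at a hold is likely: there are weekly clinician calls, participants are asked to report side effects at once, they carry a wallet card with contact details, the team meets weekly on safety, adverse events must be attributed by an investigator, and the principal investigator holds safety authority with an independent monitor assisting. All of this stands, and it lowers the risk. None of it is attached to the restart decision, however. The weekly meeting may fall after day 4, and the monitor's scheduled review is quarterly.

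A second argument is that the wording is graded: significant pain means pause and re-challenge, and only severe pain raises the question of pancreatitis. That reading is possible, but the protocol defines neither term, so staff cannot apply the distinction reliably.

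Third, the numbers are weak. Any periodic lab schedule will miss most 4-day windows, equal weighting of days ignores the clustering of side effects that first-month titration would lead one to expect, and the 14% to 79% range is too wide to inform. This is fair. The window figures show only that routine labs cannot stand in for a for-cause draw, and the hold probabilities carry no part of the conclusion.

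Fourth, the dehydration overlap is narrow: both sections stop the drug at first, and they differ only on restarting. That is true, but re-exposure is the decision at issue.

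**Conclusion.** The concern holds on both counts and should be fixed. As written, restart after a hold for abdominal pain depends only on the participant's willingness, and no section requires the enzyme result that the pancreatitis stop criterion uses. Severe dehydration from nausea or vomiting is governed by two conflicting rules.

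Up to 30 treated participants fall under the restart rule. The number who would be held for abdominal pain is unknown; under the assumptions above, 0.15 to 1.5 would be expected. These are counts of holds, not of pancreatitis, and they do not measure the risk of harm. The follow-up time behind the protocol's 5% is not given. A sensible clinician would probably investigate before restarting; the point is that the protocol does not require it. No analysis is affected.

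Confidence is medium, because the conclusion rests on the body text. The cell marks in the Appendix 1 flow chart did not survive extraction, and Appendices 3 and 4 were not available, so the lab-window percentages are provisional.

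**What to change.** In Restarting the Dose, require the investigator's documented review against the stop criteria in Duration of Therapy before any restart. After a hold for abdominal pain, also require an amylase/lipase result, read against the participant's baseline value, and let the 4 days be extended if the result is not back.

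In Holding the Dose, limit the dehydration item to moderate dehydration, so that Duration of Therapy alone governs severe cases. Clinical thresholds are for the sponsor and investigator to set. The two safety-lab schedules should be reconciled in the same amendment.

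The cost is protocol wording and an occasional unscheduled draw of assays already in the panel. Some restarts will be delayed. Because the protocol lists raised lipase as common, some participants without pancreatitis will have a high value, so the result should inform the investigator's judgement and not act as an automatic bar.

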## **Safety Laboratory Procedures and Assessments**

Participants' screening/baseline laboratory assessment will include amylase/lipase, creatinine/GFR, lipid profile, TSH, hemoglobin A1c, AST/ALT, calcitonin and hematocrit. If participants' screening laboratories are not within normal range, (they will be excluded from participation in the study.) they will be assessed by the study investigators and decision about participation in the study will be determined on an individual basis. For example, if the AST/ALT are greater than 3x the upper limit of normal the subject will not be included in the study.

- Participants' screening visit will also include a questionnaire to assess suicidality and depression, using the Patient Health Questionnaire (PHQ-9) (Appendix 2). Because the co-occurrence of depression is higher in individuals with obesity, we anticipate that many of our subjects may have minimal to mild depression. Subjects will be excluded from participation in the study if the result of the screen is greater than or equal to 10 (moderate to severe depression). They will also be referred to a psychologist if they score  $\geq 10$ . Any concern for suicide or self harm will be immediately addressed by implementing emergency petition (EP) procedures and/or calling 911.

Obese participants being treated with Liraglutide will have weekly phone calls with the study physicians or nurse practitioner to monitor for any adverse effects. In addition, during the first week, the study physicians or nurse practitioner will follow-up with the participant with two additional phone calls to answer any questions he/she may have about medication administration as well as to discuss any potential side effects.

Participants will be provided with contact information should they need to contact the study physicians or nurse practitioner at any time throughout the study. The participants will be asked to report any side effects or worsening of depression, suicidal thoughts or behavior, and/or any unusual changes in mood or behavior, to the study physicians or nurse practitioner right away.

Obese participants being treated with Liraglutide will have safety laboratory assessments performed at the following interval time points: week 0 (screening labs as above) and week 12-16 (end of study). These labs will include amylase, lipase, AST,

ALT, calcitonin and a urine pregnancy test. During phone sessions at weeks 4 and 8 to monitor for any adverse events, study personnel will also administer the PHQ-9 to again assess suicidality and any changes in mood. The PHQ-9 will also be administered at the at the second food snack task (week 12-16, end of study). Since the questionnaire relies on patient self-report, all responses will be verified by the PI and the PI will contact the subject to assess whether they need intervention and determine if they can continue in the study or if the drug should be discontinued. If at any time the subject scores  $\geq 10$  on the PHQ-9, they will be referred to a psychologist, and any concern for suicide or self harm will be immediately addressed by implementing emergency petition (EP) procedures and/or calling 911.

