## Eating Behavior Assessments

To assess food preference and food intake before vs. after liraglutide intervention, eating behavior will be assessed in three ways;

**Lab-based Food Brunch Task:** At baseline and during the last week of treatment, each participant will undergo the food brunch task. Participants will be given the opportunity to eat ad libitum for 30 minutes with detailed measurement of food/drink consumed and video recording to assess eating topography. We will obtain signed permission prior to any video recording and the participant will know when they are being videotaped. The videotape recording will be used for research only. The recording will not be shown to the general public and will not be identified with the subject's name, although their face may be included in the recording. Declining to be videotaped will not affect the participant's study participation or

treatment in any way.

The food brunch task is adapted from [name] on the basis of previous work on exposure to food cues and foods in the laboratory, which indicates that sufficient quantities, multiple food options and sufficient time available for eating are important variables modulating food intake. In the food brunch task, participants will be presented with a choice of the following foods, presented in 6 discrete bowls: skittles, M&Ms, chips, pretzels, cookies and popcorn. They will be offered the food and drinks and allowed to eat and drink as much as they like for 30 minutes. Video recordings will be assessed for frequency of times each bowl is touched/reached for, frequency of pick-ups and number of bites taken. The type and amount (weight and kilocalories) of food/drink consumed by each subject will be assessed before and after each session. All remaining items will be weighed by trained staff in the Yale Center for Clinical Investigation Metabolic Kitchen.

The instructions will state: "There are different foods and drinks on the tray. We will leave these here for you and you can eat and drink as much or as little as you like during the next half hour". We will draw labs at the following time intervals during the food brunch task: 0, 15 and 30 minutes.

Participants will also be asked to complete the following questionnaires during each food snack test visit at 4 time points (baseline and then q 10 minute intervals): Hunger Scale, Anxiety Scale, DES-R and Food Craving Scale.

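### The last scheduled PHQ-9 interval is 3–4 weeks in a 12-week course but 7–8 weeks in a 16-week course; a PHQ-9 at the week 12 call would restore even spacing

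*Combined protocol and SAP*

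**What the plan says.** **Scheduled PHQ-9.** Safety Laboratory Procedures and Assessments places the first PHQ-9 at screening, where a score of 10 or more excludes. On treatment, the text says "During phone sessions at weeks 4 and 8 to monitor for any adverse events, study personnel will also administer the PHQ-9". The last one is then fixed to a visit: "The PHQ-9 will also be administered at the at the second food snack task (week 12-16, end of study". Eating Behavior Assessments dates that visit: "At baseline and during the last week of treatment, each participant will undergo the food brunch task". Duration of Therapy allows 12 to 16 weeks of liraglutide.

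**What the PHQ-9 is used for.** Discontinuing Liraglutide covers the case where a subject's "mood changes while participating in the study, as assessed by PHQ-9": the PI contacts the subject, judges whether intervention is needed, and decides whether the drug continues. The safety section adds PI verification of responses and referral to a psychologist at a score of 10 or more. Warnings and Precautions lists suicidality among the drug's warnings.

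**What else runs alongside.**
- Calls: "Obese participants being treated with Liraglutide will have weekly phone calls with the study physicians or nurse practitioner to monitor for any adverse effects".
- Self-report: participants are asked to tell the study clinicians promptly of "worsening of depression, suicidal thoughts or behavior, and/or any unusual changes in mood or behavior".
- Emergency rule: "any concern for suicide or self harm will be immediately addressed by implementing emergency petition (EP) procedures and/or calling 911".
- Dose hold: the triggers in Holding the Dose include "Other side effects which the participant attributes to starting study drug".
- In-person contact: a second CGM is placed at 8 weeks and removed after 14 days, and the second OGTT is at week 10.

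Apart from the calls at weeks 4 and 8, none of these contacts is said to include a PHQ-9.

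**The concern.** The two fixed on-treatment checks are four weeks apart. For a 12-week course the end-of-study PHQ-9 keeps roughly that spacing. For a longer course it does not, because the final check moves with the end of treatment and nothing is added in between. Participants with the longest exposure therefore have the longest stretch without a scheduled structured check.

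What is at stake is detection of mood change or self-harm thoughts. The PHQ-9 is itself self-report. What it adds to the weekly calls is a fixed set of questions, including one that asks directly about self-harm (item 9, Appendix 2), with PI verification and a referral threshold. The calls are described only as monitoring adverse effects, with no mood or self-harm questions specified.

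The population makes this relevant. The protocol expects many participants to have minimal to mild depression, scores of 5–9 do not exclude, and 15–17-year-olds are eligible.

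**Working it through.** The documents state no interval length, so there is no figure of theirs to reproduce. The check is schedule arithmetic.

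**Inputs**
- On-treatment PHQ-9 at weeks 4 and 8 (Safety Laboratory Procedures and Assessments).
- Final PHQ-9 at the second food task (same section), which falls in the last week of treatment (Eating Behavior Assessments).
- Treatment length L = 12 to 16 weeks (Duration of Therapy).
- 30 obese participants receive liraglutide (Study Population).

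**Formulas**
- The final PHQ-9 is at elapsed week t, with t between L − 1 and L.
- Last interval as written = t − 8.
- With a PHQ-9 added at week 12, the intervals after week 8 are 12 − 8 = 4 and t − 12.
- Comparison interval = 8 − 4 = 4 weeks.

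| L (weeks) | Final PHQ-9, t | Last interval as written | Intervals with week 12 added | Longest after week 8, with week 12 added |
|---|---|---|---|---|
| 12 | 11–12 | 3–4 | none needed | 3–4 |
| 13 | 12–13 | 4–5 | 4, then 0–1 | 4 |
| 14 | 13–14 | 5–6 | 4, then 1–2 | 4 |
| 15 | 14–15 | 6–7 | 4, then 2–3 | 4 |
| 16 | 15–16 | 7–8 | 4, then 3–4 | 4 |

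**Sensitivity to the exact day.** Let the week 8 call fall on any of days 50–56 and the final task on any of days 7L − 6 to 7L.
- L = 12: (78 − 56)/7 = 3.1 to (84 − 50)/7 = 4.9 weeks.
- L = 16: (106 − 56)/7 = 7.1 to (112 − 50)/7 = 8.9 weeks.

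The contrast between short and long courses does not depend on how the weeks are counted.

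**Other contact in the interval.** The second CGM comes off at week 8 + 14/7 = 10, and the OGTT is also at week 10. From there to the final task, t − 10 is 1–2 weeks for L = 12 and 5–6 weeks for L = 16. The text names no in-person contact in that stretch, but the weekly calls continue.

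**Dose in the interval.** Table 1 reaches 3.0 mg on day 29, so on the standard schedule all the time after week 8 (day 56) is at full dose. With slower titration, which the plan allows, some dose increases could fall after week 8.

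**Questionnaires added.** One per participant continuing past week 12. That number is not given and lies between 0 and 30, so the total is 0 to 30.

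**The case against.** The strongest reply is that this is a preference about spacing. The protocol never promises a PHQ-9 every four weeks; that standard comes from a single fixed interval. Checks at weeks 4 and 8 cover the end of titration and the first month at full dose, which is a defensible choice, and nothing in the documents says that mood risk rises after week 8. Current depression, suicidal ideation and psychiatric medication are exclusions. Team meetings discuss safety weekly, and an independent monitor reviews adverse events quarterly. All of this stands, and it limits the point to a small improvement.

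Four stronger readings are tempting, and the documents do not support them.

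- **That participants go unmonitored for up to two months.** The weekly calls, self-report, dose-hold and emergency rules continue. The text does not bar an unscheduled PHQ-9: the provisions on mood change and on a score of 10 or more carry no week limit. The gap is in the scheduled structured check only.
- **That a PHQ-9 score stops the drug, so that a missed PHQ-9 means a missed stop.** The questionnaire prompts PI contact and the PI decides. Emergency action needs no PHQ-9 at all.
- **That the form's two-week recall should cover the whole course.** In a 16-week course, 7–8 minus 2 gives 5–6 weeks after week 8 outside recall. But the week 4–8 interval already leaves 4 − 2 = 2 weeks outside, and the fix would still leave 2 + (1 to 2) = 3–4. Continuous coverage is not an aim of the protocol.
- **That the flow chart confirms the gap.** Its PHQ-9 marks are lost in the copy reviewed. The column headings that survive run weekly only to weeks 9–11 and then go to Visits 3 and 4. This is consistent with a schedule not extended for longer courses but does not prove it, since the visit columns may be meant to cover weeks 12–16. A mark at weeks 9–11 or Visit 3 would shorten the interval.

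One part of the reply does not stand: that the weekly calls already do the job. The protocol adds the PHQ-9 to the calls at weeks 4 and 8, so its authors did not treat an ordinary call as a substitute.

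**Conclusion.** The point holds for the schedule as the text gives it. The last scheduled PHQ-9 interval is 3–4 weeks for a 12-week course and rises to 7–8 weeks for a 16-week course, against 4 weeks between the two fixed checks. A reader should not infer a broken rule, an absence of monitoring or a biased analysis; none of these follows.

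The conclusion rests on three assumptions. The food snack task and the food brunch task are the same procedure, since the protocol uses the two names interchangeably. Appendix 1 schedules no further PHQ-9. The participant completes the planned course: those who withdraw are asked for end-of-study questionnaires, which could bring the last check forward. How many participants would be treated past week 12 is unknown (0 to 30), so the practical size of the benefit is unknown too.

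It is worth making as a cheap improvement to patient safety, because it concerns a listed drug warning and uses the protocol's own tool.

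**What to change.** In Safety Laboratory Procedures and Assessments, add a PHQ-9 at the week 12 phone call for any participant continuing liraglutide past week 12, unless the second food task falls in that week. Mark the same time point in Appendix 1. The verification, referral and emergency rules already in the section would apply unchanged.

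For a 16-week course the longest scheduled interval falls from 7–8 weeks to 4. The gain is even spacing of the structured check.

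The cost is at most 30 nine-item phone questionnaires over the whole study, each with PI verification. The weekly calls are already required for participants on liraglutide, so no new visit, call or staff is needed.
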